In the Phase III PREVAIL trial [Beer et al, 2014], 1717 men without prior chemotherapy exposure were randomized to receive enzalutamide or placebo. Compared to placebo, enzalutamide improved rPFS (rPFS rate at 12-month: 65% vs 12%; HR= 0.19; 95% CI, 0.15 to 0.23; P<0.001) and overall survival (HR=0.71; 95% CI, 0.60 to 0.84; P<0.001). The

benefit of enzalutamide was shown with respect to all secondary endpoints, including the time until the initiation of cytotoxic chemotherapy (HR= 0.35), the time until the first skeletal-related event (HR= 0.72), a complete or partial soft-tissue response (59% vs. 5%), the time until PSA progression (HR, 0.17), and a rate of decline of at least 50% in PSA (78% vs. 3%) (P<0.001 for all comparisons). Fatigue and hypertension were the most common clinically relevant adverse events associated with enzalutamide treatment.

No clinical data are available on activity of enzalutamide after sequential treatment with enzalutamide and chemotherapy. Modest activity of enzalutamide after therapy with abiraterone acetate and docetaxel were reported. The reported rate of ≥50% PSA decline range between13% to 46% [Bianchini et al, 2014; Azad et al, 2014; Schrader et al, 2014].

Clinical prevalence of biomarkers implicated in resistance has been reported. Approximately 30-40% patients have circulating tumor cells positive for ARv7 after enzalutamide or AA therapy [Antonarakis et al, 2014]. No PSA response was observed on either enzalutamide or abiraterone among these patients. ARv567es was reported to be expressed in at least 1 metastatic lesion among 71% of 13 subjects who underwent biopsy [Sun et al, 2010].

Rationale for Enzalutamide re-treatment

Benefit of re-treatment with a molecularly targeted agent after intervening therapies that are not cross-resistant with the initial therapies have been observed in other tumor types such as epidermal growth factor receptor (EGFR) tyrosine kinase inhibitor and in EGFR- mutant non-small cell lung cancer [Riely et al, 2007; Song et al, 2013].

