7.4.3 Analysis of Exploratory Endpoints

Descriptive statistics (e.g., N, mean, standard deviation, minimum, median, maximum, frequency, and percentage) will be provided for baseline blood and plasma samples and by each post-baseline scheduled timepoint.

Baseline biomarker measurements will be included in regression models to assess correlation with the following endpoints: rPFS, time to OS, PSA30, PSA50, PSA90, and objective response. Time-to-event data endpoints will be modelled via Cox proportional hazards model. Binary endpoints will be modeled via logistic regression. Univariate models will be used to assess significance of individual biomarker measures. Multivariable models may also be considered to control for baseline demographic, disease, and treatment characteristics.

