3.2 Study Design

This is a US-based, multicenter, open-label, single-arm, study evaluating the efficacy, safety, and tolerability of open-label enzalutamide in the re-treatment setting. A total of 40 patients will be enrolled. Patients must have been previously treated with enzalutamide in the pre-chemotherapy setting for a minimum of 8 months, followed by docetaxel for a minimum of 6 cycles. Exposure to intervening systemic anti-cancer therapies such as abiraterone prior to docetaxel is allowed. Subjects will receive treatment with open-label enzalutamide (160 mg daily), administered as four 40 mg capsules, by mouth, once daily, until radiographic or clinical progression (such as pathological fracture, cord compression, worsened pain requiring radiation therapy, or opioid analgesic dose increase or initiation), or unacceptable toxicity. Per the Investigator's clinical judgment and with sponsor approval, patients may be allowed to continue enzalutamide until the next treatment is initiated. If another non-cytotoxic, non-investigational, antineoplastic agent is initiated after protocol-defined progression has been determined, enzalutamide may be continued per the Investigator's clinical judgment and with sponsor approval as long as the patient is tolerating enzalutamide and continues androgen deprivation therapy.

The consensus guidelines of the Response Evaluation Criteria in Solid Tumors (RECIST) 1.1 and the Prostate Cancer Clinical Trials Working Group 2 (PCWG2) will be utilized to determine radiographic disease progression. Radiographic disease progression is defined by RECIST 1.1 for soft tissue disease. Bone disease progression is considered when a minimum of two new lesions are observed. Progression on bone scan at time points prior to or at week 9 requires a confirmatory scan performed six or more weeks later. This confirmatory

scan should demonstrate at least 2 additional new lesions compared to the Week 9 scan (PCWG2).

The following assessments of prostate cancer status will be collected during the course of the trial: soft tissue disease on computed tomography (CT) scan or on magnetic resonance imaging (MRI), bone disease on radionuclide bone scans, and PSA.

Throughout the study safety and tolerability will be assessed by the recording of adverse events, monitoring of vital signs, physical examinations, and safety laboratory evaluations.

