5.4 Biomarker Analysis Set (BAS)

The Biomarker analysis set (BAS) consists of the subset of the FAS population for which biomarker data are available to facilitate derivation of at least one of the correlative biomarkers. The Total N used in summaries and analyses for each unique biomarker will be the number of subjects with data available for that unique biomarker.

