Three baseline continuous log base 2 transformed neuroendocrine predictors: 1) CgA, 2) NSE, and 3) synaptophysin will be assessed individually, as independent variables, to predict rPFS, time to PSA progression, OS, and composite progression free survival (cPFS) using a single variable Cox model.

Hazard ratio point estimates, n, standard errors, p-values, and 90% confidence intervals will be displayed in a single table for all the AR, inflammatory cytokine, and neuroendocrine Cox models.

KM plots, medians, and 90% confidence intervals for the binary AR predictors will be presented for rPFS, time to PSA progression, OS and cPFS.

Waterfall plot of maximum reduction in PSA from baseline with AR-v7, AR-v12, and AR mutation status labeled on the plot.

The AR-V7 and the composite AR-V7/V12 composite predictors will be individually assessed as an independent variables to predict PSA30, PSA50, PSA90, and objective response using Fisher's exact test. Note that objective response will be evaluated using subjects that are both BAS and have measureable disease.

Counts, frequencies, differences in frequencies and 90% Clopper-Pearson methodology will be displayed for the binary AR predictors.

Reported p-values for hazard ratios will use Wald (chi-square) test statistics, and p-values for comparing Kaplan-Meier curves will use log-rank (score) test statistics. Breslow method will be used for handling ties.

In the event that additional exploratory analyses are required for the Clinical Study Report, the SAP will be amended accordingly.

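### The AR-V7 and PSA-response association is tested only on three cuts of one continuous measure; adding an estimate on the log-ratio scale would be a cheap gain for this exploratory analysis

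*SAP*

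**What the plan says.** The synopsis of the protocol lists, among its correlative objectives, exploring how resistance biomarkers relate to rPFS, PSA response and PSA progression. For PSA response, SAP 7.4.3 takes AR-V7 and the AR-V7/V12 composite, each to be "individually assessed as an independent variables to predict PSA30, PSA50, PSA90, and objective response using Fisher's exact test". SAP 6.1.2 defines PSA30, PSA50 and PSA90 from the same quantity, the decline at the lowest post-baseline PSA. SAP 7.4.3 also plans a "Waterfall plot of maximum reduction in PSA from baseline with AR-v7, AR-v12, and AR mutation status labeled on the plot", with no estimate, interval or test attached.

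Protocol 7.4.3 handles the same outcomes differently ("Binary endpoints will be modeled via logistic regression"), but also after dichotomising. SAP 7.4.3 adds counts, differences in frequencies and 90% Clopper-Pearson intervals for the binary predictors, and SAP 7.8 repeats PSA30 by AR-V7 subgroup.

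On numbers, "A total of 40 patients will be enrolled", and SAP 5.4 makes the biomarker set the "subset of the FAS population for which biomarker data are available", so 40 is a ceiling. Neither document gives a significance level, power or target effect for these tests.

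**The concern.** Cutting a continuous outcome discards information, and with at most 40 men split unevenly by AR-V7 status little can be spared. Fisher's exact test adds a further loss because it is conservative in small tables. The variable that would recover the information has to be derived for the waterfall plot anyway. Three overlapping tests also leave the reader with three cut-specific differences and no single summary of how far AR-V7 moves PSA. If no continuous comparison is pre-specified, one may be chosen after the labelled waterfall plot has been seen.

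**Working it through.** **The plan's own figure.** The documents give no power for this association. Their one sizing figure is about 34 rPFS events. With L = ln2/4 per month, P(event) = 1 − [exp(−12L) − exp(−24L)]/(12L) = 1 − (0.125 − 0.0156)/2.079 = 0.947, and 40 × 0.9 × 0.947 = 34.1. That reproduces, but says nothing about biomarker tests.

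**Inputs from the documents.** N is at most 40. Protocol 1.2: "Approximately 30-40% patients have circulating tumor cells positive for ARv7 after enzalutamide or AA therapy". That gives 12 positive and 28 negative at 30%, or 16 and 24 at 40%.

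**Assumptions.** Two-sided 0.10, to match the 90% intervals; PSA50 rates by AR-V7 status as shown; the shape of the PSA distribution.

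**Fisher thresholds.** With no responders among the positives, the negatives must show at least 7 of 28 (p = 0.081) or 5 of 24 (p = 0.071) for p < 0.10, and 9 of 28 (p = 0.037) or 7 of 24 (p = 0.029) for p < 0.05.

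**Shift model.** Let Y = log2(lowest post-baseline PSA/baseline PSA), normal with SD 1. PSA50 means Y ≤ −1, so the group mean is −1 − z(p), where p is the PSA50 rate. For 20% v 3% the means are −1 + 0.842 = −0.158 and −1 + 1.881 = 0.881, a shift of 1.04. PSA30 means Y ≤ log2(0.7) = −0.515, so its rates are Φ(−0.357) = 36% and Φ(−1.396) = 8%. PSA90 means Y ≤ −3.32, and even the negatives reach it in about 0.1%.

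Fisher power is the sum over all (a, b) of Bin(a; n₁, p₁) × Bin(b; n₂, p₂) where the Fisher p-value is at most 0.10. Power of the continuous test is simulated, with error of about one point.

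| PSA50, negative v positive | Fisher PSA30 | Fisher PSA50 | Fisher PSA90 | Continuous test |
|---|---|---|---|---|
| 20% v 3% | 52–60% | 23–36% | about 0% | about 88–93% |
| 30% v 5% | 68–74% | 49–58% | about 0% | 93–96% |
| 30% v 15% | about 25% | 18–21% | about 0% | 39–47% |

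Ranges cover the two splits. Against the best cut, PSA30, the gap is 33–36, 22–25 and 14–22 points in the three rows.

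**Can the three cuts together make up the loss?** A second run put SD 1 on the natural-log scale, with a 1 SD shift, PSA50 of 30% in negatives and a 12/28 split. Fisher power was 55%, 43% and 0% for PSA30, PSA50 and PSA90; Wilcoxon had 87% and a t-test 89%. Counting a result if any cut is significant gives 63%, with a true error rate of about 13%. A single Fisher test at nominal 0.10 had a true size of only 4–7%.

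**All-or-none model.** Here only a fraction of AR-V7-negative men respond (ln ratio mean −1.5, SD 0.5) and everyone else is alike (mean 0.2, SD 0.4). No positive responds. Two-sided 0.10:

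| Split | Responders among negatives | Fisher PSA50 | Welch, log ratio | Wilcoxon |
|---|---|---|---|---|
| 12/28 | 20% | 27% | 54% | 24% |
| 12/28 | 30% | 67% | 81% | 43% |
| 12/28 | 46% | 95% | 98% | 79% |
| 16/24 | 20% | 46% | 53% | 27% |
| 16/24 | 30% | 78% | 79% | 46% |
| 16/24 | 46% | 97% | 97% | 81% |

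Welch gains 0 to 27 points over Fisher. Wilcoxon is 3 to 32 points below Fisher here (about 2 to 30 in a repeat run).

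**The case against.** The plan follows its own definition: PSA response is PSA30/50/90 throughout both documents, the analysis is labelled exploratory, and no power is claimed. The continuous data will be visible in the waterfall plot, and each cut has a planned difference in frequencies, so effect sizes are not absent. All of that stands, and it limits the weight of the point. The large gaps also rest on a normal, equal-variance shift that the documents do not supply. The one relevant finding cited in Protocol 1.2, "No PSA response was observed on either enzalutamide or abiraterone among these patients", fits an all-or-none effect at least as well. This stands too, and it decides the form of the remedy.

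Three stronger readings are tempting and not supported:

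- **The Fisher tests can hardly detect even an extreme effect.** A reader might set the thresholds of 7 of 28 (25%) and 5 of 24 (21%) against the bottom of the range in Protocol 1.2 ("The reported rate of ≥50% PSA decline range between13% to 46"%). That range is an overall rate for enzalutamide after abiraterone and docetaxel, not a rate in AR-V7-negative re-treated men. If positives never respond, 13% overall implies 0.13 × 40/28 = 18.6% or 0.13 × 40/24 = 21.7% in negatives, where exact Fisher power at 0.10 is 25% or 62%. At 0% v 30% it is 78–89%, and at 0% v 46% it is above 99%.
- **A null result would say nothing about AR-V7 resistance.** SAP 7.4.3 also relates AR-V7 and the composite to rPFS, time to PSA progression, OS and cPFS by Cox models, some adjusted for AR-FL.
- **The Fisher tests should give way to a rank test.** The all-or-none table shows that this could lose power.

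**Conclusion.** The narrower point holds. The SAP's only tests of AR-V7 against PSA response use dichotomised outcomes, and the underlying continuous change is plotted without an estimate. Under a shift model the cost against the best planned cut is about 14 to 36 points of power in the scenarios shown, and PSA90 contributes essentially nothing. Under an all-or-none effect the gain from a Welch comparison is smaller, 0 to 27 points over Fisher on PSA50, and a rank test does worse than Fisher. A comparison of mean log ratios is therefore the sounder addition under both mechanisms.

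These sizes depend on the assumed distribution, the assumed response rates, the 0.10 level and the full 40 men; the documents fix only the ceiling of 40 and the 30–40% prevalence. For the weaker effect (30% v 15%) even the continuous test stays below 50%, so the addition improves the analysis without making it decisive. This is a cheap improvement to an exploratory analysis, to consider rather than require.

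**What to change.** Add to SAP 7.4.3, for AR-V7 and separately for the composite, one pre-specified comparison of mean log2(lowest post-baseline PSA/baseline PSA) by baseline biomarker status. Use a Welch comparison or a linear model, and back-transform the difference to a ratio with its 90% CI. Give a Wilcoxon rank-sum test as a sensitivity check and do not name it the lead analysis. Keep the planned PSA30/50/90 Fisher tests and the differences in frequencies. The same edit can reconcile Fisher's test in the SAP with logistic regression in the protocol.

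The cost is one paragraph and one short procedure on a variable already needed for the plot, with no new data. The downside is one more exploratory estimate and p-value per predictor. The change should be made before database lock and before the labelled waterfall plot is reviewed.

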7.4.4 Analysis of Other Variables

Not Applicable.

7.5 Analysis of Safety

All analysis of safety will be presented for SAF, unless specified otherwise.

7.5.1 Adverse Events

An overview table will include the following details:

- Number of TEAEs,
- Number and percentage of subjects with TEAEs,
- Number of drug related TEAEs,
- Number and percentage of subjects with causally drug related TEAEs,
- Number of serious TEAEs,
- Number and percentage of subjects with serious TEAEs,
- Number of serious drug related TEAEs,
- Number and percentage of subjects with serious drug related TEAEs,
- Number of TEAEs leading to permanent discontinuation of study drug,
- Number and percentage of subjects with TEAEs leading to permanent discontinuation of study drug, and
- Number of deaths.

The number and percentage of subjects with TEAEs, as classified by SOC and PT will be summarized. Summaries will be provided for:

- TEAEs,
- TEAEs by NCI CTCAE grade
- drug related TEAEs,
- serious TEAEs,
- serious TEAE by NCI CTCAE grade
- drug related serious TEAEs,
- drug related serious TEAEs by NCI CTCAE grade
- TEAEs leading to permanent discontinuation of study drug,
- drug related TEAEs leading to permanent discontinuation of study drug,
- TEAEs excluding serious adverse events that equal to or exceed a threshold of 5.0%, and
- common TEAEs that equal to or exceed a threshold of 5.0 %.

The number and percentage of subjects with TEAEs, as classified by PT only, will be summarized in descending frequency.

The number of TEAEs and the number and percentage of subjects with TEAEs, as classified by SOC and PT will also be summarized by NCI CTCAE grade to study drug. In the subject count, if a subject has multiple TEAEs with the same SOC or PT, but with differing severity, then the subject will be counted only once with the worst severity, however, if any of the severity values are missing then the subject will be counted only once with missing severity. In the adverse event count, the adverse events will be presented in each category they were classified to. Drug related TEAEs will be presented in a similar way by severity only.

TEAEs of special interest will be summarized by the number and percentage of subjects with the following AEs: fatigue, fall, hypertension, non-pathological fractures, cognitive/memory impairment, loss of consciousness, neutropenia, and convulsion.

7.5.2 Clinical Laboratory Evaluation

Quantitative clinical laboratory variables, i.e., hematology, biochemistry, and urinalysis will be summarized using mean, standard deviation, minimum, maximum and median at each visit. Additionally, a within-subject change will be calculated as the post-baseline measurement minus the baseline measurement and summarized in the same way. Baseline is defined as the last available measurement prior to the first study drug dose.

Frequency tabulations of qualitative clinical laboratory variables (urinalysis) will be presented at each visit.

Laboratory results will also be graded using NCI-CTCAE, where possible. Parameters that have criteria available for both low and high values, i.e., hypo- and hyper-, will be summarized for both criteria. The same subject can be counted for both values if the subject has different laboratory values meeting each criterion. NCI-CTCAE grade of laboratory evaluations will be summarized by number and percentage of subjects for each visit. Shift

tables of lab parameters NCI-CTCAE grade change from baseline to worst post-baseline grade will also be presented.

7.5.2.1 Liver Enzymes and Total Bilirubin

The following potentially clinically significant criteria for liver tests – defined as Alkaline Phosphatase (ALP), Alanine Transaminase (ALT), total bilirubin, Aspartate Transaminase (AST) and their combination are defined. The subject's highest value during the investigational period will be used.

Parameter	Criteria
ALT, AST, Total Bilirubin	$\geq 2\times\text{ULN}$
	$\geq 3\times\text{ULN}$
	$\geq 5\times\text{ULN}$
ALT or AST	$\geq 2\times\text{ULN}$
	$\geq 3\times\text{ULN}$
	$\geq 5\times\text{ULN}$
ALT and/or AST	(ALT and/or AST $\geq 3\times\text{ULN}$) and total bilirubin $\geq 2\times\text{ULN}$

And Total Bilirubin(*)

(*) Combination of values measured within same sample

The number and percentage of subjects with potentially clinically significant values in liver function tests during the investigational period will be presented.

The number and percentage of subjects with potentially clinically significant values in liver enzyme and total bilirubin tests during the investigational period will be presented.

7.5.3 Vital Signs

The baseline visit is the last measurement taken prior to initial study drug administration.

Vital signs (systolic blood pressure, diastolic blood pressure, ECG parameters (collected only at baseline/screening), and pulse rate) will be summarized using mean, standard deviation, minimum, maximum and median by visit. Additionally, a within-subject change will be calculated per visit as the post-baseline measurement minus the baseline measurement and summarized.

Tables for potentially clinically significant vital signs will be generated using baseline value for each subject for each treatment group.

The following potentially clinically significant criteria are defined for each parameter:

Vital Sign Variable	Criteria
SBP	≥ 180 mmHg AND ≥ 20 mmHg change from baseline
DBP	≥ 105 mmHg AND ≥ 15 mmHg change from baseline
Pulse Rate	≥ 120 bpm AND ≥ 15 bpm change from baseline

7.5.4 Electrocardiograms (ECGs)

No post baseline ECG is collected. Not applicable.

7.5.5 Pregnancies

Not applicable.

7.5.6 Other Safety-Related Observations

ECOG PS will be summarized by counts and frequencies by visit

7.6 Analysis of PK

Not applicable.

7.7 Analysis of PD

Not applicable.

7.8 Subgroups of Interest

rPFS, time to PSA progression, and PSA30 will be analyzed for the subgroups defined on the basis of the categorized variables at baseline listed below:

- Ensure to capture subgroups from AFFIRM, plus the following groups of interest to this study
- CTC detected (yes vs no)
- AR-v7 (yes vs no)
- Prior abiraterone
- PSA90 on prior enzalutamide
- Prior enzalutamide treatment duration > median
- PSA50 on prior docetaxel
- Prior docetaxel treatment duration \geq median

7.9 Other Analyses

Not applicable.

7.10 Interim Analysis (and Early Discontinuation of the Clinical Study)

An interim efficacy analysis with no adjustments will be conducted using a cutoff date corresponding to the week 13 visit of 40th subject to report internally on PSA response rates for internal review.

7.11 Handling of Missing Data, Outliers, Visit Windows, and Other Information

Refer to the data specification document in which more details are provided.

7.11.1 Missing Data

As a general principle, no imputation of missing data for other variables will be done. Exceptions are the start and stop dates of AEs and concomitant medication. If day is missing from any date in a derivation then calculate the derived value using 15th day of month. If month or year is missing from any date in a derivation then set the derived value to missing.

Adverse events with missing relationship will be summarized as 'Related to Study Drug'. Adverse events with missing severity grade will be handled as 'missing'.

Incomplete onset dates default AEs to treatment emergent. Listings of the AEs and concomitant medications will present the actual partial dates; imputed dates will not be shown.

Cases where the onset date of an AE is (partially) missing, will be addressed prior to or during the DRM in order to determine whether the AE must be considered treatment emergent or not.

Imputation on missing date of initial diagnosis (cancer duration) and cancer treatment history (start date, stop date, or date of procedure) will be done as follows:

- Incomplete Day: use the 15th day of the month
- Incomplete Month: use 1st of July if the Year is before Year of dosing, otherwise missing.
- Incomplete Year: no imputation, the derived variable is considered to be missing.

Imputation methods will not be used to determine other endpoints.

Listings will always show the original date information without imputation, but derived parameters (TEAE indicator, start day, end day, study day) will be flagged.

